## 5.0 Stratification Factors:

This Phase 2 randomized study will compare radioactive iodine (RAI) in combination with placebo or selumetinib for the treatment of RAI-avid recurrent/metastatic thyroid cancers. A 1:1 randomization will be used, where the Pocock-Simon algorithm (Pocock SJ et al, 1975) will be used to balance the arms with respect to the following stratification factors, along with the registering membership:

- Prior thyroid cancer treatment with systemic chemotherapy and/or molecularly targeted inhibitors: Yes vs. No
- Age  $\geq 70$  years: Yes vs. No
- Bone Metastases present: Yes vs. No
- Previous  $^{131}\text{I}$  therapy given for thyroid remnant ablation prior to this study: Yes vs. No
- Measureable disease (as defined by this protocol): Yes or No

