16.0 Statistical Considerations and Methodology

## 16.1 Study Overview

This randomized, double-blind Phase II trial will compare the response rate at 6 months after therapy with  $^{131}\text{I}$  in combination with placebo or selumetinib for the treatment of patients with RAI A recurrent and/or metastatic thyroid cancer. Historical response rate to a single dose of RAI can be difficult to estimate from retrospective data that include heterogeneity with regards to the extent of disease treated, RAI doses administered, patient preparation, response assessments etc. Nonetheless, a retrospective analysis has demonstrated that the response rate for first-line  $^{131}\text{I}$  therapy alone for recurrent/metastatic RAI A thyroid cancer with measurable disease is generally around 20% (Sabra et al., 2013). We estimate that patients with non-measurable disease and with the serum thyroglobulin criteria described in this protocol will have a response rate of approximately 50%. Anticipating that 40% of the patients accrued will have measurable disease and 60% with non-measurable disease only (requiring serum TG measurements to be used in response assessment), the predicted response rate for this population would be 40%. It is hoped that the combination of selumetinib and  $^{131}\text{I}$  can increase the response rate to 65%.

This trial will also compare the best overall response rate, progression-free survival (PFS), changes in serum thyroglobulin levels and adverse event rates between the two treatment arms. In addition, we will explore the genomic and transcriptomic landscape of RAI A tumors for signatures that correlate to therapeutic benefit achieved in patients with RAI-avid recurrent and/or metastatic thyroid cancer treated with  $^{131}\text{I}$  in combination with placebo or selumetinib.

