## 16.2 Primary Endpoint

The primary endpoint for this study will compare the response rate with  $^{131}\text{I}$  in combination with placebo or selumetinib for the treatment of patients with RAI A recurrent and/or metastatic thyroid cancer at the 6-month time point (“6-month time point” refers to the assessments designated to occur approximately 6 months after  $^{131}\text{I}$  therapy in combination with placebo or selumetinib has been administered, which may be 6 months +/- 1 week from the time therapeutic RAI is administered. For patients with non-measurable disease, TG values obtained outside this window may be allowed if repeat measurements were required to ensure the this value was obtained in the context of a TSH  $\leq 0.4$ ).

A patient will be classified as a responder if they have a partial or complete response at the 6-month time point when compared to the baseline, pre-study radiologic scan(s) according to the criteria outlined in Section 11.0 (confirmation of response is not required). The proportion of patients with a response will be calculated and compared between the 2 arms using a Chi-square or Fisher’s Exact test. All eligible patients who are randomized and begin treatment will be evaluable for the primary endpoint.

It is possible that patients will have clinical, radiologic, or biochemical evidence of disease progression early in the study and still demonstrate benefit from the study treatment later in the study for several reasons: 1) selumetinib alone prior to RAI may not have significant clinical efficacy, 2) Thyrogen™ stimulation can transiently increase tumor size which can be mistaken for disease progression; 3) the therapeutic effects of RAI can be delayed; and 4) evidence of progression may be evident prior to administration of RAI. Hence, patients with evidence of radiographic or clinical PD noted prior to the 6-month time point assessment may remain on study and continue to receive treatment and/or be evaluated for response at the discretion of the treating physician. The final objective response assessment at 6 months for these patients will be based upon a comparison between the 6-month radiologic scan(s) (and serum thyroglobulin,

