if applicable) and the baseline, pre-study radiologic scans (and serum thyroglobulin, if applicable). However, if in the opinion of the treating physician these patients are unlikely to demonstrate benefit at the 6-month time point, the patients will be considered to have had a progression/death event, categorized as non-responders, and taken off the study.

Patients who receive additional treatment for their thyroid cancer outside of this protocol prior to the 6-month time point (except for thyroid hormone TSH suppression, palliative radiation to a non-target lesion, or therapy to prevent pathologic fractures caused by bone metastases (e.g. zoledronic acid and denosumab)) will be considered non-responders.

**Final Analysis for Primary Endpoint:** The primary goal is to compare  $^{131}\text{I}$  in combination with placebo or selumetinib where the alternative hypothesis is that selumetinib and  $^{131}\text{I}$  has an improved confirmed response rate compared to placebo plus  $^{131}\text{I}$ . Twenty-eight evaluable patients will be enrolled to each arm, for 56 evaluable patients, total. With this sample size, we will be able to detect a significant difference between a response rate of 40% in the control group vs. 65% in the experimental group (odds ratio for response of 2.786, with 1-sided type I error = 0.15 and power = 80%). All patients who meet the eligibility criteria, sign the consent form, are randomized, and start treatment will be evaluable.

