### 16.3 Secondary Endpoints

The following endpoints will be compared between the 2 arms: best overall response, 6- month progression-free survival, changes in serum thyroglobulin levels, and adverse event rates between the 2 treatment arms. All patients who meet the eligibility criteria, sign the consent form, are randomized, and start any treatment will be considered evaluable for the endpoints below.

**Best overall response:** The best overall response will be compared between the two according to the criteria outlined in Section 11.0. This comparison will be done using a chi-square test. For a patient to be classified as a response, they need a partial or complete response that is confirmed at least 4 weeks later anytime during the study.

**Progression-Free Survival:** Progression-free survival (PFS) is defined as the time from study entry to the first of either disease progression or death from any cause, where disease progression will be determined based on criteria outlined in Section 11.0. PFS will be estimated using the Kaplan-Meier method, where the log-rank test will be used to compare the 2 treatment arms. Evidence of progression noted from the time of registration to within 6 months after  $^{131}\text{I}$  therapy may be disregarded as a progression event if the treating physician feels it is reasonable according to the rationale detailed in Section 16.2. The response assessment at 6 months for these patients will be based upon a comparison between the 6-month radiologic scan(s) and the baseline, pre-study radiologic scans. In addition, the 6-month PFS rate will also be compared between the arms.

**Serum Thyroglobulin Levels:** Changes in thyroglobulin will be assessed. The Wilcoxon Rank-Sum test will be used to compare the changes in thyroglobulin (pre-RAI and post-RAI) between the two treatment arms. (This analysis will not be possible for patients with detectable thyroglobulin antibodies.)

**Adverse events:** The maximum grade for each type of adverse event will be summarized using CTCAE version 4.0. The frequency and percentage of grade 3+ adverse events will be compared between the 2 treatment arms. Comparisons between arms will be made by using either the Chi-square or Fisher's Exact test.

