#### 16.5 Total Sample Size

A maximum of 56 evaluable patients (28 per arm) will be accrued onto this randomized phase II study unless the study is closed early for excessive toxicity. We anticipate accruing an additional 5% of patients to account for ineligibility, cancellation, major treatment violation, or other reasons. Therefore, maximum accrual is 60 patients (30 per arm).

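### The response and PFS analyses leave out measurable disease, a balancing factor with planned control response of 20% vs 50%, so their result depends on the realised split between arms

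*Combined protocol and SAP*

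**What the plan says.** Section 5.0 lists five balancing factors in addition to registering membership. One of them is "Measureable disease (as defined by this protocol): Yes or No". Section 6.22 confirms that the Pocock-Simon procedure balances the margins of these factors.

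Section 16.1 builds the control rate from the same factor: about 20% response with measurable disease and about 50% without. It continues: "Anticipating that 40% of the patients accrued will have measurable disease and 60% with non-measurable disease only". Sections 11.43 and 11.44 give the two groups different criteria. With measurable disease, partial response is a fall of at least 30% in summed lesion dimensions. With non-measurable disease only, and structural findings that are neither complete response nor progression, partial response is a thyroglobulin fall of 50% or more, and a thyroglobulin rise of 25% or more counts as progression.

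The primary analysis in 16.2 reads "The proportion of patients with a response will be calculated and compared between the 2 arms using a Chi-square" or Fisher's exact test. In 16.3, best overall response is compared by chi-square. PFS is estimated by Kaplan-Meier, "where the log-rank test will be used to compare the 2 treatment arms". Section 16 names no stratified or adjusted analysis and no reporting of response by measurable disease.

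**The concern.** The design treats measurable disease as important enough to balance on and assumes a 30-point gap in control response between its two levels. The analysis then ignores it. Pocock-Simon balancing over six factors holds each margin roughly, not exactly, equal. If the control arm has a few more measurable-disease patients, the unstratified comparison reads part of that difference as benefit from selumetinib; if the selumetinib arm has them, a real benefit is partly hidden.

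Measurable disease also decides which endpoint definition a patient is judged by. A pooled response rate without stratum-specific rates cannot show whether a difference comes from tumour shrinkage or from a fall in thyroglobulin.

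**Working it through.** **Inputs.** From 16.2: 28 evaluable patients per arm (56 in all); planned response 40% on control and 65% on selumetinib; and the error and power settings, given as "odds ratio for response of 2.786, with 1-sided type I error = 0.15 and power = 80" (the last figure in per cent). From 16.1: control response 20% (measurable) and 50% (non-measurable), mix 40:60. Then 0.40 × 56 = 22.4, so perfect balance is about 11 measurable and 17 non-measurable patients per arm.

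**Step 1: the plan's own figure.** For a one-sided test with pooled variance and no continuity correction,

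n per arm = [z₀.₈₅ √(2p̄q̄) + z₀.₈₀ √(p₁q₁ + p₂q₂)]² / (p₂ − p₁)²

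With p̄ = 0.525, this is [1.036 × √0.49875 + 0.842 × √0.4675]² / 0.0625 = 27.3, so 28. Power at 28 is 80.6%. The odds ratio is (0.65/0.35)/(0.40/0.60) = 2.786. The stated design reproduces.

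**Step 2: shift in the estimate.** With no treatment effect and d more measurable patients in control than in selumetinib, the expected unadjusted difference is (0.50 − 0.20) × d/28:

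- d = 1: 1.1 points
- d = 2: 2.1 points
- d = 4: 4.3 points

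The target is 25 points and the standard error is about 12.5 points.

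**Step 3: exact one-sided size, given the split.** This enumerates four binomials, with response 20% and 50% in both arms. Chi-square (uncorrected) and CMH reject at z ≥ 1.036; Fisher rejects at p ≤ 0.15.

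| Measurable, control v selumetinib | Chi-square | Fisher | CMH |
|---|---|---|---|
| 11 v 11 | 15.6% | 9.7% | 15.6% |
| 12 v 11 | 17.7% | 11.2% | 16.3% |
| 11 v 12 | 13.5% | 8.2% | 14.7% |
| 12 v 10 | 20.1% | 13.0% | 14.0% |
| 10 v 12 | 11.8% | 7.0% | 15.2% |
| 13 v 9 | 25.4% | 17.0% | 15.1% |
| 9 v 13 | 8.7% | 5.0% | 14.9% |

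**Step 4: exact power, given the split.** Assume a gain of 25 points in each stratum (20% to 45%, 50% to 75%).

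| Split | Chi-square | Fisher | CMH |
|---|---|---|---|
| 11 v 11 | 84.5% | 76.7% | 84.5% |
| 10 v 12 | 79.9% | 71.0% | 82.7% |
| 9 v 13 | 74.6% | 64.7% | 82.5% |

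CMH power stays at about 82–85% over all seven splits of Step 3.

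**Step 5: averages over the allocation.** The protocol gives no favoured-arm probability, so values of 0.8, 0.9 and 1.0 were assumed, with assumed prevalences for the other factors and 8 memberships (12,000 simulated trials per setting).

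- Type I error: chi-square 15.6–16.1%, CMH 15.5–15.6%.
- Mean absolute imbalance in measurable patients: 0.9–1.5 (95th percentile 2–4), against 2.9 (95th percentile 7) under simple randomisation.
- Standard deviation of the estimated difference: 0.124–0.127 unstratified, 0.122–0.126 stratified.
- Average power at a common within-stratum odds ratio of about 3.44: chi-square 87–88%, CMH about 87%.

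A separate simulation (assumed probability 0.85, 12 memberships, 25 points in each stratum) gave average power of 83.8% for chi-square and 83.0% for CMH. Counts differed by 2 or more in 34% of its trials.

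**The case against.** The strongest reply is that the planned error rate is a property of the whole procedure, allocation included, and that rate is not materially moved. Sizes above and below 15% at opposite imbalances roughly cancel. This stands. A reader might infer from the 20.1% that the planned test fails to control type I error; Step 5 does not support that.

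Further points also stand:

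- The allocation already restrains this imbalance. A two-patient difference moves the estimate by about 2 points, small beside a standard error of about 12.5.
- Fisher's test is also permitted, and at 12 v 10 it stays below 15%. Inflation at that split depends on which permitted test is used.
- The 34% frequency rests on assumed settings and should not be read as a property of this trial.
- The 20% and 50% are response rates at the planning stage, and the 50% is the authors' own estimate. No PFS or best-response rates by measurable disease are given. No other balancing factor is given rates, so measurable disease cannot be ranked as the strongest predictor.
- A stratified pooled test still combines two response definitions. Only reporting by stratum addresses that, with about 11 measurable patients per arm.

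The objection does not remove the case for prespecifying. One trial yields one split, visible in the baseline table, and an adjusted analysis chosen after seeing it would be post hoc. Balance is set at randomisation, while the evaluable set drops ineligible and untreated patients, which can loosen it.

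**Conclusion.** The concern holds as a conditional one. The analysis omits a factor that the design balances on, that the plan assumes separates control response by 30 points, and that selects the endpoint criteria. At a two-patient imbalance, chi-square size moves from 15.6% to 20.1% or 11.8%, while CMH gives 14.0% or 15.2%. These figures assume that 20%/50% is right and that 28 per arm are analysed. The frequency of such splits cannot be fixed from the documents.

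A reader might infer that stratifying would raise power or that the sample size is wrong. Neither follows: average power is the same to within about 1 point, and 28 per arm reproduces. For PFS and best overall response the consequence is unquantified and rests only on the differing criteria. This is a sensible change to prespecify, not a flaw that invalidates the design.

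**What to change.** In 16.2, make the primary test a one-sided Cochran-Mantel-Haenszel test at 0.15, stratified by measurable disease (Yes/No) as recorded at randomisation. Report the stratum-adjusted risk difference and each arm's response rate within each stratum. Keep the unstratified comparison as supportive. Naming one test also settles the open choice between chi-square and Fisher, which matters in itself: with 40% response in both arms, exact size is 17.0% against 11.0%, and power at 40% v 65% is 83.4% against 75.7%.

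In 16.3, stratify the best-overall-response comparison and the log-rank test by the same factor.

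The cost is a few lines of text and at most about 1 point of average power (about 84% v 83%). The factor is already collected and 28 per arm is unchanged.

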#### 11.22 Non-Measurable Disease

11.221 All other lesions (or sites of disease (e.g., visible pulmonary nodules  $<1$  cm in longest diameter)) are considered non-measurable disease. Bone lesions, leptomeningeal disease, ascites, pleural/pericardial effusions, lymphangitis cutis/pulmonis, inflammatory breast disease, and abdominal masses (not followed by CT or MRI), are considered as non-measurable as well.

Note: 'Cystic lesions' thought to represent cystic metastases can be considered as measurable lesions, if they meet the definition of measurability described above. However, if non-cystic lesions are present in the same patient, these are preferred for selection as target lesions.

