#### 11.42 Non-Target Lesions & Non-Target Lymph Nodes

Non-measurable sites of disease (Section 11.22) are classified as non- target lesions or non-target lymph nodes and should also be recorded at baseline. These lesions and lymph nodes should be part of the response assessment as detailed in Section 11.433 or 11.442.

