#### 11.434 Overall Objective Status for Patients with Measureable Target Lesions/Lymph Nodes

The overall objective status for an evaluation is determined by combining the patient's status on target lesions, target lymph nodes, non-target lesions, non-target lymph nodes, and new disease as defined in the following tables. Serum thyroglobulin measurements will not be used in determining overall response, except for designating a complete response (as detailed in Section 11.432 and in the table below):

Target Lesions & Target Lymph Nodes	Non-Target Lesions & Non-Target Lymph Nodes	New Sites of Disease	Overall Objective Status
CR	CR	No	CR*
CR	Non-CR/Non-PD	No	PR
PR	CR Non-CR/Non-PD	No	PR
CR/PR	Not All Evaluated**	No	PR***
SD	CR Non-CR/Non-PD Not All Evaluated**	No	SD
Not all Evaluated	CR Non-CR/Non-PD* Not All Evaluated**	No	Not Evaluated (NE)
PD	Unequivocal PD CR Non-CR/Non-PD Not All Evaluated**	Yes or No	PD
CR/PR/SD/PD/Not all Evaluated	Unequivocal PD	Yes or No	PD
CR/PR/SD/PD/Not all Evaluated	CR Non-CR/Non-PD Not All Evaluated**	Yes	PD

\* CR designation may also require serum thyroglobulin assessment as detailed in Section 11.432.

\*\* See Section 11.431

\*\*\* NOTE: This study uses the protocol RECIST v1.1 template dated 2/16/2011. For data collection and analysis purposes the objective status changed from SD to PR in the ACCRU protocol RECIST v1.1 template as of 2/16/2011 and to match RECIST v1.1 requirements.

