#### **Overall Objective Status for Patients with Non-Measurable, Non-Target Lesions/Lymph nodes**

The overall objective status for an evaluation is determined by:

- Structural assessment of lesions/lymph nodes as detailed in Section 11.442.
- For the “non-CR/non-PD” structural category, measurement of the serum TG in the context of suppressed TSH (and negative TG antibody) will be used to determine the final response designation (the exception is for the assessment of complete response, which requires measurement of a stimulated TG, see chart below).

Non-Target Lesions & Non-Target Lymph Nodes	Serum Thyroglobulin (TG)* (or TG antibody)	New Sites of Disease	Overall Objective Status
CR	TG < 0.2 ng/ml on TSH suppression* OR stimulated TG < 0.1 ng/ml (see 11.442)	No	CR
CR	TG ≥ 0.2 ng/ml on TSH suppression* OR stimulated TG > 0.1 ng/ml (see 11.442)	No	Assess as per Non-CR/Non-PD
Non-CR/Non-PD	50% or more reduction compared to baseline Tg WITHOUT a 25% or more increase compared to the lowest TG measured on study (baseline or nadir)*	No	PR
Non-CR/Non-PD	25% or more increase compared to the lowest TG measured on study* (baseline or nadir)	No	PD
Non-CR/Non-PD	Less than 50% reduction compared to baseline TG WITHOUT a 25% or more increase compared to the lowest TG measured on study* (baseline or nadir)	No	SD
Non-CR/Non-PD	New detection of TG antibody	No	PD
Not All Evaluated	25% or more increase compared to lowest TG measured on study Tg* (baseline or nadir)	No	PD

Non-Target Lesions & Non-Target Lymph Nodes	Serum Thyroglobulin (TG)* (or TG antibody)	New Sites of Disease	Overall Objective Status
Not All Evaluated	WITHOUT 25% or more increase compared to lowest TG measured on study Tg* (baseline or nadir)	No	NE
Uequivocal PD	Any serum TG result or TG antibody result, including failure to complete the measurement as per protocol	Yes or No	PD
CR Non-CR/Non-PD Not All Evaluated	Any serum TG or TG antibody result, including failure to complete the measurement as per protocol	Yes	PD
CR Non-CR/Non-PD Not All Evaluated	TG was not evaluated or not evaluated in the context of TSH suppression*	No	NE

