\* TG will be measured in the context of a suppressed TSH ( $\leq 0.4$  mcU/ml) and negative TG antibody, except for the designation of CR which may require TG measurement in the context of TSH stimulation (see 11.442). For the primary endpoint, the serum TG value designated for the 6-month assessment (6 months after therapeutic  $^{131}\text{I}$  is administered) will be used. If the 6-month serum TG is initially measured in the context of a TSH  $>0.4$  mcU/ml, then every effort should be made to repeat this assessment until a serum TG value is obtained in the context of a TSH  $\leq 0.4$  mcU/ml, even if it requires obtaining the measurement outside of the protocol-defined  $\pm 1$  week window. Serum TG values that have to be obtained outside this protocol-defined window to ensure it is measured in the context of TSH  $\leq 0.4$  mcU/ml will still be used for the primary assessment of response.

11.45 **NOTE:** On this study, patients with clinical, radiographic, or biochemical (i.e., thyroglobulin, if applicable) evidence of progression of disease (as described above) on assessments prior to the 6-month disease evaluation (i.e. the scans and evaluations performed 6 months after therapeutic  $^{131}\text{I}$  is administered) will be allowed to continue on study treatment and/or evaluations given the potentially delayed therapeutic benefit of  $^{131}\text{I}$ , effects of Thyrogen™, etc. For patients with clinical, radiographic or biochemical evidence of progression of disease on assessments prior to the 6 month disease evaluation, the final objective response assessment at 6 months will be based

upon a comparison between the 6 month radiologic scan(s)/evaluations and the baseline, pre-treatment radiologic scans (and serum thyroglobulin measurements if applicable).

11.46 Symptomatic Deterioration: Patients with global deterioration of health status requiring discontinuation of treatment without objective evidence of disease progression at that time, and not either related to study treatment or other medical conditions, should be reported as PD due to “symptomatic deterioration.” Every effort should be made to document the objective progression even after discontinuation of treatment due to symptomatic deterioration. A patient is classified as having PD due to “symptomatic deterioration” if any of the following occur that are not either related to study treatment or other medical conditions:

- Weight loss >10% of body weight.

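### Does exempting palliative radiation to non-target lesions let off-protocol treatment count as primary response in patients with non-measurable disease only?

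*Combined protocol and SAP*

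**What the plan says.** Section 16.2 (Primary Endpoint) counts a patient as a non-responder if further thyroid cancer treatment is given outside the protocol before the 6-month assessment, "except for thyroid hormone TSH suppression, palliative radiation to a non-target lesion, or therapy to prevent pathologic fractures caused by bone metastases".

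Whether a lesion is non-target depends on measurability. Section 11.42 states: "Non-measurable sites of disease (Section 11.22) are classified as non- target lesions or non-target lymph nodes". Section 11.22 lists among the non-measurable sites "Bone lesions, leptomeningeal disease, ascites, pleural/pericardial effusions".

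Response is then decided differently in the two strata:

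- **Measurable disease (Section 11.434).** Partial response rests on the sum of target-lesion dimensions. "Serum thyroglobulin measurements will not be used in determining overall response, except for designating a complete response".
- **Non-measurable disease only (Section 11.443).** When the structural category is neither complete response nor progression, "measurement of the serum TG in the context of suppressed TSH (and negative TG antibody) will be used to determine the final response designation". Partial response is a fall of at least 50% from baseline without a 25% rise from the lowest value.

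Some rules override a thyroglobulin fall. Unequivocal structural progression is progression whatever the thyroglobulin shows ("Any serum TG result or TG antibody result, including failure to complete the measurement as per protocol"). A new site of disease is also progression, and so is "New detection of TG antibody" when the structural category is neither complete response nor progression. For patients with earlier signs of progression, Section 11.45 says that "the final objective response assessment at 6 months will be based" on a comparison with baseline.

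Section 16.1 expects 60% of patients to have non-measurable disease only, with a control response rate of about 50%. Section 16.2 plans one comparison of proportions by chi-square or Fisher's exact test. Section 16 describes no sensitivity analysis.

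**The concern.** In measurable disease the limit to non-target lesions does useful work. The lesions that decide response may not be irradiated without the patient becoming a non-responder, and thyroglobulin matters only for complete response.

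In patients with non-measurable disease only there is no target lesion, so the limit excludes nothing. Their partial response usually rests on one serum value for the whole patient, which cannot leave out an irradiated site. A patient irradiated for symptoms, without progression at 6 months and with thyroglobulin down by half, is a responder. None of the overriding rules mentions radiation.

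If this happened often enough, part of the primary response in the larger stratum would come from treatment outside the protocol. The single planned comparison would not show it. With 28 patients per arm, one patient is 1/28 = 3.6 percentage points, so even a few such cases deserve a check.

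**Working it through.** **The plan's own figure.** Inputs from Section 16.2: 40% v 65%, one-sided type I error 0.15, power 80%. Pooled-variance formula without continuity correction:

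n = [z(0.85)·√(2·p̄·q̄) + z(0.80)·√(p₁q₁ + p₂q₂)]² / (p₂ − p₁)²

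With p̄ = 0.525: (1.036 × 0.706 + 0.842 × 0.684)² / 0.0625 = 27.4, so 28 per arm. Power at 28 is 80.6%. The odds ratio is (0.65/0.35)/(0.40/0.60) = 2.786. Both stated figures reproduce.

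**Size of the stratum.** 0.60 × 28 = 16.8 patients per arm.

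**Assumptions, because the documents give no values.** Let r be the share of the stratum irradiated before 6 months, c the share of otherwise non-responding irradiated patients whom radiation turns into responders, and p the response rate without radiation. Take p = 50% on placebo (Section 16.1) and 75% on selumetinib (assumed, adding the design's 25 points).

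**Errors under the plan's rule and under the strict alternative** (irradiated patients scored as non-responders):

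- Plan's rule, false responders per arm = 16.8 × r × (1 − p) × c.
- Strict rule, true responders lost per arm = 16.8 × r × p.

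Radiation equal in both arms, applied to 40% v 65%:

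| r | c | False responders, placebo / selumetinib | Power, plan's rule | True responders lost by strict rule, placebo / selumetinib | Power, strict rule |
|---|---|---|---|---|---|
| 10% | 30% | 0.25 / 0.13 | 79.7% | 0.84 / 1.26 | 77.1% |
| 20% | 30% | 0.50 / 0.25 | 78.7% | 1.68 / 2.52 | 73.7% |
| 20% | 60% | 1.01 / 0.50 | 76.7% | 1.68 / 2.52 | 73.7% |

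For the first row, placebo becomes 0.40 + 0.60 × 0.10 × 0.50 × 0.30 = 0.409 and selumetinib 0.65 + 0.60 × 0.10 × 0.25 × 0.30 = 0.6545, giving 79.7%. At r = 2%, c = 30%, power is 80.4%. With no drug effect and equal r and c, the arms have equal rates and the rejection rate stays at 15.0%.

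**Radiation in one arm only** (0.25, 0.50 or 1.0 false responders):

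- Placebo only: power 78.6%, 76.6% or 72.1%.
- Selumetinib only, true rates 40% v 40%: rejection rate 16.6%, 18.4% or 22.2%.

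**When the strict rule makes fewer errors.** This needs r·p < r·(1 − p)·c, that is c > p/(1 − p). The threshold is 1.0 at p = 50% and 3.0 at p = 75%, neither of which a proportion can exceed. It is 0.43 at an assumed p = 30%. The strict rule also distorts the result if use is one-sided: one true responder lost on selumetinib only lowers power to 71.9%, and one lost on placebo only raises the rejection rate under 40% v 40% to 22.3%.

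**The case for a change.** The best case for acting is that the textual gap is certain, only its size is unknown, and a pre-specified check is cheap while one chosen after unblinding would be post hoc. The word palliative limits the intent of radiation, not the site or its effect on thyroglobulin. Blinding and balanced allocation do not rule out chance imbalance with about 17 patients per arm. With 11 of 28 control responders, the uncorrected one-sided test needs 15 on selumetinib, a margin of four patients. Taking c = 100% as an upper bound, with rates of 38% v 63% (the Section 16.1 mix, 0.4 × 20% + 0.6 × 50% = 38%, plus 25 points), radiation in 10% or 20% of the stratum in both arms gives power of 77.2% or 73.7%. If it fell on selumetinib alone and the drug had no effect, the rejection rate would be 21.0% or 28.1%.

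The reading of the text stands, and so does the arithmetic. What does not follow is that the proposed check would answer the question. Scoring irradiated patients as non-responders mostly reclassifies people who would have responded anyway, so a difference from the primary result would not show dependence on radiation.

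The extreme figures also need a single palliated site to carry whole-patient thyroglobulin past a 50% fall in every case, which nothing in the documents supports. Section 18.1 lists the RT Material form only at end of treatment, but the same table has an Evaluation/Observation form during observation. The content of neither is given, so missing data capture cannot be inferred.

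**Conclusion.** No change to the plan follows. The exemption is written into the same sentence as the non-responder rule, and with Section 11.42 it gives one definite score for an irradiated patient with non-measurable disease only. A sentence saying that it covers all lesions in that stratum would repeat what the text already yields. Making such patients non-responders in the primary analysis would exchange one error for another that is larger in every row of the table.

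With similar use in both arms, which double-blinding and balancing on bone metastases and measurability (Section 5.0) make the reasonable expectation, the cost is 0.9 points of power at r = 10%, c = 30% and 3.9 points at r = 20%, c = 60%. The type I error is unaffected under no drug effect. These sizes rest on assumed values of r and c and on an assumed 75% response rate on selumetinib in this stratum. The one-arm figures are possible by chance, but the documents give no reason to expect them.

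Applying Section 16.2 already requires the analysts to know who received radiation and to which lesion. The trial report can therefore state how many patients were irradiated before the 6-month assessment, by arm and measurability, with their response status. That is ordinary descriptive reporting.
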